4.3.9. Need for renal replacement therapy

The probability of requiring renal replacement therapy between randomization and Day 30 will be estimated for each treatment group by the proportion of individuals randomized to each group requiring renal replacement therapy between randomization and Day 30. The primary analysis will be based on a 2-sided Wald test of the null hypothesis that the probability of requiring renal replacement therapy is the same among individuals receiving CCP or standard of care. The percent relative risk reduction will be estimated along with a 95% confidence interval.

4.3.10. Myocarditis

The probability of developing myocarditis over the first 30 days will be estimated in a similar fashion to the way that the need for ECMO and renal replacement therapy are estimated and tests of effects will likewise be reported in a similar fashion.

4.3.11. Patient-reported outcomes (PROs)

The original responses from each patient will be converted into a single utility index score anchored at 0 for dead and 1 for full health using the scoring algorithm based on Canadian society preferences. Utility changes from baseline to Day 30 were estimated by analysis of covariance adjusting for baseline utilities and compared between the two arms.

4.3.12. Incremental cost per quality-adjusted life year (QALY)

In addition to the cost of CCP, we will estimate the cost associated with the stay in ICU, hospitalization, use of ventilator and ECMO, diagnostics and procedures, and medications. The difference in cost between CCP and standard care will be divided by the difference in QALY calculated using the EQ-5D-5L to derive the incremental cost per QALY for CCP. 95% confidence interval for the incremental ratio will be assessed using a non-parametric bootstrapping with replacement approach with B=1000 times.

4.3.13. CPP transfusion-associated adverse events at Day 30

Adverse events judged to be definitely or probably related to CPP will be analyzed two ways: 1) using the Common Terminology Criteria for Adverse events (CTCAE; Grading 1-5)); and using the ISBT definitions for acute transfusions reactions (Grades 1-4). (Protocol section 4.3.13),

1. CTCAE Grading: The proportion of individuals experiencing CPP transfusion-associated adverse events (CTCAE Grades 1-5) will be reported overall by type, and severity. The total number of CPP transfusion-associated adverse

events will also be tabulated overall by type, and severity which will accommodate the possibilities of multiple adverse events per individual.

2. ISBT Grading: The proportion of individuals experiencing CPP transfusion-associated adverse events (ISBT Grades 1-4) will be reported overall by type, and severity. The total number of CPP transfusion-associated adverse events will also be tabulated overall by type, and severity which will accommodate the possibilities of multiple adverse events per individual.

4.3.12. Grade 3, 4, and 5 adverse events at Day 30

See protocol section 9 for additional details regarding AE definitions.

The proportion of individuals experiencing Grade 3, 4 or 5 (as per CTCAE criteria) adverse events will be analyzed overall and by treatment arm by type, severity grade, and expected/unexpectedness. The total number of Grade 3, 4 or 5 adverse events will also be tabulated overall and by treatment arm by type, severity grade and expected/unexpected which will accommodate the possibilities of multiple events per individual.

4.3.13. Grade 3, 4 and 5 serious adverse events at Day 30

Serious adverse events (unexpected and meeting criteria for expedited reporting to the sponsor, Hamilton Health Sciences) will be analyzed as summarized below. TRALI and TACO adverse events, while not technically considered SAEs, require expedited reporting to the sponsor; hence they will be also be included.

The number and proportion of individuals experiencing a serious adverse event will be reported by event type, overall and by treatment arm. A second analysis will be by event which will accommodate the possibilities of multiple events per individual.

In the interim and final analyses, the relative risk reduction for death (CCP versus standard of care) will be computed along with a 95% confidence interval. The relative risk reduction (CCP versus standard of care) will also be computed for SAEs (regardless of outcome) along with a 95% confidence interval.

The cumulative incidence of serious adverse event will also be plotted by treatment group.

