12. STATISTICAL CONSIDERATIONS

12.1. Sample Size Considerations

Assuming a baseline risk of intubation or death by Day 30 of 30% in hospitalized patients with standard of care, a sample size of 1200 (800 in the CCP arm, and 400 in the standard of care arm) would provide 80% power to detect a relative risk reduction of 25% with CCP therapy using a 2-tailed test at level α = 0.05. This assumes no patient is lost to follow-up. Lost follow-up is expected to be minimal.

There is uncertainty about the intubation and mortality rate that will be observed in this study due to possibly evolving profile of COVID-19 patients admitted hospital over the course of the pandemic. To address this, a blinded sample-size re-estimation will take place when the primary outcome is available for 50% of the target sample. Sample size will only be adjusted if the estimated event rate is different than the originally specified event rate to a sufficient extent that the study is not expected to achieve the desired nominal power for the test of the primary outcome.

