1.3. Sample Size Justification

Assuming a 30% risk of the composite outcome of intubation or death by Day 30 among hospitalized patients under standard of care, a sample size of 1200 individuals (800 in the CCP arm, and 400 in the standard of care arm) will provide 80% power ($\beta = 0.20$) to detect a relative risk reduction of 25% with CCP therapy using a 2-tailed test at level $\alpha = 0.05$. We assume that no patient will be lost to follow-up.

2. Responses

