2.2.11. Patient-reported outcomes (PROs)

PRO will be measured using a widely used generic instrument called EQ-5D-5L. It measures health-related quality of life in five dimensions, namely, mobility, self-care, usual activities, pain/discomfort, and anxiety/depression. Patients can report five level impairment, reflecting no, slight, moderate, severe, and extreme problems in each dimension. The EQ-5D-5L will be administered at baseline and Day 30.

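### SAP 4.3.12 names no baseline adjustment for the QALY difference; adjusting for baseline EQ-5D-5L utility would make it more precise using data already collected

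*SAP*

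**What the plan says.** SAP 2.2.12 and Protocol 12.4.2 set a 30-day horizon for the cost-utility analysis. SAP 4.3.12 (the section on incremental cost per QALY; the number is used again later for adverse events) lists the cost items. It then says that the cost difference is "divided by the difference in QALY calculated using the EQ-5D-5L to derive the incremental cost per QALY for CCP", with a non-parametric bootstrap of 1000 resamples for the interval of the ratio. It names no covariate and no regression, and it does not say how a patient's QALY is built from the utilities or how a death enters.

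Utility is observed twice. SAP 2.2.11 says: "The EQ-5D-5L will be administered at baseline and Day 30". The schedule of assessments in Protocol 8.3 requires the baseline questionnaire on Day 1, after consent and before plasma. Protocol 8.4 lists it among procedures done after randomization.

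SAP 4.3.11 scores death as 0 and full health as 1, and says that utility changes are "estimated by analysis of covariance adjusting for baseline utilities and compared between the two arms". Nothing carries that adjustment over to 4.3.12.

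**The concern.** With two measurements, the natural 30-day QALY for a patient alive at Day 30 is the average of the two utilities times 30/365. Half of that weight falls on a value recorded before plasma is given, so the treatment cannot change it. Variation in baseline utility then adds noise to the QALY difference without adding information about treatment, and any chance imbalance between 800 and 400 patients passes directly into the denominator of the ratio. A ratio with a small, noisy denominator is awkward to interpret, so avoidable noise there is worth removing. The SAP already accepts baseline adjustment for this instrument one section earlier.

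**Working it through.** **The plan's own figure.** The documents give no standard deviation, standard error or power for QALYs. The arm sizes and design effect used below come from the primary calculation in SAP 1.3, which states that "a sample size of 1200 individuals (800 in the CCP arm, and 400 in the standard of care arm) will provide 80% power". Its inputs are a 30% control-arm risk, a 25% relative reduction, two-sided 0.05 and no loss to follow-up. Event rates are 0.30 and 0.30 × 0.75 = 0.225; the pooled rate is (400 × 0.30 + 800 × 0.225)/1200 = 0.25.

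- Null SE = √[0.25 × 0.75 × (1/400 + 1/800)] = 0.02652
- Alternative SE = √[0.30 × 0.70/400 + 0.225 × 0.775/800] = 0.02726
- Power = Φ[(0.075 − 1.96 × 0.02652)/0.02726] = Φ(0.845) = 80.1%

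The stated 1200 and 80% reproduce.

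**QALY formula (assumed).** For Day 30 survivors, Q = (30/365) × (U0 + U30)/2. Let s0 and s30 be the standard deviations of utility at baseline and Day 30, and ρ their correlation. Apart from the squared time factor, the variances per patient are:

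- unadjusted: (s0² + s30² + 2ρ·s0·s30)/4
- adjusted for U0: s30²(1 − ρ²)/4
- gap: (s0 + ρ·s30)²/4

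The gap is never negative, is positive at ρ = 0, and vanishes only if ρ = −s0/s30.

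**Baseline contribution alone.** The arm-size factor is √(1/800 + 1/400) = 0.06124. With s0 = 0.2 to 0.3 (assumed), the SE from baseline is s0 × 0.06124/2 × 30/365 = 0.0005 to 0.00075 QALY.

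**Survivors only, both standard deviations 0.25 (assumed).** The ratio of adjusted to unadjusted SE is √[(1 − ρ)/2]: 0.71 at ρ = 0, 0.59 at 0.3, 0.50 at 0.5 and 0.39 at 0.7. At ρ = 0.5 the SE falls from 0.00109 to 0.00054.

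**With deaths.** Deaths add variance that baseline utility explains poorly, so the gain shrinks. The table comes from a simulation with 1,000,000 patients per setting. It assumes mean utilities 0.5 and 0.7, both standard deviations 0.25 before truncation to −0.15 to 0.95, death times uniform over Days 2 to 30 and unrelated to baseline utility, and utility falling linearly to 0 at death.

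| Mortality | ρ | SE unadjusted | SE adjusted | Reduction |
|---|---|---|---|---|
| 10% | 0 | 0.00105 | 0.00087 | 17% |
| 10% | 0.5 | 0.00118 | 0.00085 | 28% |
| 20% | 0 | 0.00119 | 0.00106 | 11% |
| 20% | 0.5 | 0.00130 | 0.00105 | 19% |
| 25% | 0 | 0.00124 | 0.00112 | 10% |

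If lower baseline utility also raises the risk of death, the gain is larger. Over all settings of this simulation with 10% to 25% mortality, the reduction is 10% to 36%.

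**Wider range.** The answer also depends on mean utilities. Take baseline SD 0.2 to 0.3, Day 30 SD 0.25, ρ 0 to 0.5, mortality 10% to 20%, and means of 0.3 to 0.7 at baseline and 0.6 to 0.8 at Day 30. The reduction then runs from roughly 5% (high means, small baseline SD, ρ = 0, 20% mortality) to roughly 35% (low means, large baseline SD, ρ = 0.5, 10% mortality). If utility stays flat until death, the top of the range is about 43%. Adjustment helped in every setting.

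**The case against.** The case against has several parts, and most of it limits the claim without removing it.

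- *A reader might infer that the SAP prescribes a raw difference in means.* It does not say so. It is silent on adjustment and on the formula, and the half weight rests on assumed linear interpolation and applies to Day 30 survivors. Taken literally, the section still specifies nothing beyond a difference, so the adjustment needs writing in.
- *A reader might infer that 4.3.11 and 4.3.12 contradict each other.* They do not. One compares utility change at Day 30 and the other forms a cost per QALY ratio. Unadjusted comparison is also the SAP's habit elsewhere, for example for the primary outcome, ventilator-free days and ICU days. Section 4.3.11 shows only that baseline adjustment of this instrument is already acceptable to the authors.
- *A reader might infer bias or an invalid interval.* Randomization keeps the unadjusted difference unbiased on average, and resampling patients already carries the baseline variation into the interval. The loss is in precision.
- *A reader might infer that baseline noise is a material share of any plausible effect.* That is not shown. Against a rough gain of 0.075 × 30/365 = 0.0062 QALY, the baseline SE of 0.0005 to 0.00075 is about 8% to 12%. That gain credits every avoided event with 30 days at full health and ignores gains in patients without an event, so it is only a yardstick.
- *The SAP reports an interval for the ratio.* The calculations here concern the denominator alone. A ratio whose denominator may be near zero can be unstable with or without adjustment. This objection stands.
- *The baseline questionnaire follows open-label randomization.* Knowing the allocation could affect the answers. The analysis of covariance in 4.3.11 shares this assumption, and any such distortion would also enter an unadjusted QALY difference. It is a good reason to report both estimates.

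**Conclusion.** The point holds as a matter of efficiency. Under linear interpolation, adjusting for baseline utility lowers the variance of the QALY difference and protects it from chance imbalance. The direction follows from algebra in survivors and held in every simulated setting with deaths. The size is uncertain: roughly 5% to 35% off the standard error, up to about 43% if utility is flat until death, under means, standard deviations, correlations and mortality that are all assumed. The survivors-only reductions of 29% to 61% (equal standard deviations, ρ from 0 to 0.7) should not be quoted for a trial in which deaths are expected. The documents do not support a claim of bias, of an invalid interval, or of any particular narrowing of the ratio's interval. The outcome is secondary and economic, and the primary analysis is untouched.

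**What to change.** In SAP 4.3.12:

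1. State the QALY formula: how utility is interpolated between baseline and Day 30, and how patients who die are handled, with utility 0 from death and a stated path up to death.
2. Estimate the QALY difference by regressing each patient's QALY on arm and baseline EQ-5D-5L utility, and refit that regression within each of the 1000 bootstrap samples.
3. Use the adjusted difference in the ratio and wherever incremental QALYs are reported. Give the unadjusted difference as a sensitivity result, because Protocol 8.4 places baseline procedures after open-label randomization and the schedule requires only that the questionnaire precede plasma.

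The cost is a few sentences in the SAP and a few lines of code. Baseline EQ-5D-5L is already scheduled, so no new data are needed.

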1.1. Summary of Design

This is a multi-centre open-label randomized controlled trial in which recruited patients will be randomized in a 2:1 ratio to receive either 500 mL of COVID-19 convalescent plasma (CCP) comprised of a 500 mL unit from one donor or two 250 mL units from one or two donors collected by apheresis, or standard of care. The plan is to randomize 1200 individuals to obtain an expected 800 patients in the CCP arm and 400 patients in the arm receiving standard of care.

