2.2.12. Incremental cost per quality-adjusted life year (QALY)

A cost effectiveness analysis alongside the trial will be conducted. The summary measure for the economic evaluation is incremental cost per QALY comparing CCP with standard care over the 30-day trial period.

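### The 30-day cost-per-QALY ratio divides by a QALY difference close to zero, so its bootstrap interval may not be readable; net monetary benefit from the same replicates should be pre-specified

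*SAP*

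**What the plan says.** SAP 2.2.12 fixes the measure and horizon: "The summary measure for the economic evaluation is incremental cost per QALY comparing CCP with standard care over the 30-day trial period". SAP 4.3.12, under the heading on incremental cost per QALY, defines the ratio as the between-arm cost difference over the between-arm QALY difference, with QALYs derived from the EQ-5D-5L, and adds: "95% confidence interval for the incremental ratio will be assessed using a non-parametric bootstrapping with replacement approach with B=1000 times". SAP 2.2.11 has the EQ-5D-5L measured at baseline and Day 30, and SAP 4.3.11 anchors the utility at 0 for dead and 1 for full health, using Canadian preferences. Protocol 12.4.2 names the same 30-day measure without adding a method.

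Neither document mentions net monetary benefit, a willingness-to-pay value, a cost-effectiveness plane, an acceptability curve, or what to do with replicates whose QALY difference is zero or negative. The type of bootstrap interval is not stated.

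**The concern.** A ratio is well behaved only when its denominator is clearly away from zero. Write ΔC for the cost difference and ΔQ for the QALY difference (CCP minus standard of care). As ΔQ passes through zero with ΔC positive, the ratio jumps from very large positive to very large negative. The sign of the ratio is also ambiguous:

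- Negative ratios arise when CCP is costlier and worse (dominated) and when it is cheaper and better (dominant).
- Positive ratios arise when CCP is costlier and better and when it is cheaper and worse.

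If the replicates spread across ΔQ = 0, sorting their ratios on one scale puts a dominated replicate below a costlier-and-better one, as though it were better value. Limits read from that ordering match no statement about value for money. The ratio is the only economic summary planned, so a listed secondary outcome could be reported with an interval that nobody can interpret, and with no planned alternative.

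**Working it through.** **The plan's own figure.** The documents size the trial for the primary outcome only; they give no figure for the economic analysis. SAP 1.3 has "Assuming a 30% risk of the composite outcome of intubation or death by Day 30", a "relative risk reduction of 25% with CCP therapy", two-sided α = 0.05, and states that "a sample size of 1200 individuals (800 in the CCP arm, and 400 in the standard of care arm") "will provide 80% power". SAP 1.1 gives the 2:1 allocation.

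- CCP risk = 0.30 × 0.75 = 0.225; difference = 0.075; pooled risk = (120 + 180)/1200 = 0.25.
- Pooled SE = √[0.25 × 0.75 × (1/800 + 1/400)] = 0.02652.
- Unpooled SE = √[0.225 × 0.775/800 + 0.30 × 0.70/400] = 0.02726.
- Power = Φ[(0.075 − 1.96 × 0.02652)/0.02726] = 80.1%. The stated power reproduces.

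**Ceiling on the denominator.**

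- Maximum accrual per patient = 30/365.25 = 0.082 QALY.
- If every prevented event saved all of it, ΔQ = 0.075 × 0.082 = 0.0062 QALY, about 2.2 quality-adjusted days. This takes the effect to act only through the composite and values no state below dead.
- In that extreme case QALYs are the composite rescaled, so ΔQ/SE = 0.075/0.02726 = 2.75. The chance that a 95% interval for ΔQ includes zero is then Φ(1.96 − 2.75) ≈ 21%. No assumed variance is needed for this step.

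**More realistic settings.** None of the following inputs is in the documents. QALYs were the area under the utility curve from baseline to Day 30, with 800 and 400 patients and no missing data. Assumed values:

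- baseline utility mean 0.5–0.6 (SD 0.20–0.35);
- Day 30 utility 0.70–0.85 without an event (SD 0.12–0.28) and 0.1–0.5 after intubation (SD 0.1–0.3);
- correlation between the two times 0.4;
- 30%, 50% or 80% of events fatal, with deaths uniform over Days 1–30.

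With z = ΔQ/SE, the chance that the central 95% of ΔQ includes zero is Φ(1.96 − z) − Φ(−1.96 − z). Under the planned effect (z, then chance):

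| Setting | 30% fatal | 50% fatal | 80% fatal |
|---|---|---|---|
| Low SD | 1.58, 65% | 1.85, 55% | 2.19, 41% |
| Mid | 1.45, 69% | 1.57, 65% | 2.10, 44% |
| High SD | 1.12, 80% | 1.41, 71% | 1.71, 60% |
| Event survivors nearly as badly off as dead | 2.28, 37% | 2.39, 33% | 2.47, 31% |

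ΔQ runs from 0.0015 to 0.0033 QALY and its SE from 0.0010 to 0.0014. The chance exceeds 50% in 7 of the 12 settings. At half the effect it is 80% to 91%; under no effect it is about 95%.

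**Full bootstrap.** A simulation with half of events fatal, B = 1000 and 300 trials per setting gave 59% to 72% under the planned effect. The median share of replicates with negative ΔQ was 4% to 9% under the planned effect, 17% to 30% at half the effect, and about 50% under none.

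**A stricter criterion.** Opposite quadrants giving ratios of the same sign, each holding at least 2.5% of replicates, occurred in 31% to 53% of trials under the planned effect. Under a smaller or null effect the figure was 8% to 83%, depending on the assumed plasma cost.

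**Sensitivity to the SD.** With a QALY SD of 0.02, SE = 0.02 × √(1/800 + 1/400) = 0.00122. The chance that more than 2.5% of replicates are negative is then 87%, 63%, 31% and 10% for true gains of 0.001, 0.002, 0.003 and 0.004. At a gain of 0.002 it is 10%, 41%, 63% and 74% for SDs of 0.010, 0.015, 0.020 and 0.025.

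**The case against.** A reader might infer that the interval will usually be uninterpretable. The documents do not support that for the trial's planned effect. The chance depends on utilities, their SDs and the fatal share of events, none of which is given, and it falls below one half in 5 of the 12 settings. With a larger gain or a smaller SD, the denominator can sit safely away from zero.

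A reader might also infer that the SAP prescribes naive percentile limits. It does not: it says only that the interval comes from a non-parametric bootstrap. On the text alone, the certain gap is one of specification, with no interval type and no rule for negative denominators. Percentile ranking is the assumed reading.

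The stricter criterion depends heavily on costs that the documents do not give, so it cannot carry the argument. The outcome is also the twelfth of fifteen secondary outcomes in the protocol synopsis, and no decision or stopping rule hangs on it.

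All of this limits the claim but does not remove it. The small denominator follows from the 30-day horizon and the planned effect, and a plan should give a readable result if the effect is small or absent.

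**Conclusion.** The point holds as a low-cost improvement to a secondary analysis. From the documents, the QALY difference can be at most about 0.006 through prevented events. Under the assumed utilities it lies 1.1 to 2.5 SE from zero at the planned effect. The ratio interval then has roughly an even chance of spanning a sign change in the denominator (31% to 80%), rising to 80% to 91% at half the effect and about 95% under none. These percentages rest on the assumed utilities, SDs and fatal shares; missing EQ-5D-5L data were not modelled and would widen the SE. The consequence for interpretation also rests on the percentile reading.

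No typical interval width is claimed. It would need a cost difference and a cost SD that the documents do not state, and a noisy cost difference would widen the ratio interval by itself.

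**What to change.** Amend SAP 4.3.12 to use the same 1000 replicates, with each patient's cost and QALY kept together, and report:

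1. Incremental cost and incremental QALY separately, each with a 95% CI.
2. The cost-effectiveness plane.
3. Incremental net monetary benefit, λ × ΔQ − ΔC, with a 95% CI over a pre-stated range of willingness-to-pay values λ, and the acceptability curve. This is linear in both differences, so a denominator near zero cannot disrupt it.
4. The ratio as a descriptive point estimate beside these, with its quadrant stated, and with no ratio CI when the QALY difference straddles zero. Where a ratio CI is given, name its type.

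The cost is a few sentences of SAP text and no extra data. The one real burden is naming the willingness-to-pay range with its currency and country perspective. The trial runs in four countries; SAP 4.3.11 fixes Canadian preferences for utilities, but SAP 4.3.12 states no perspective for costs.
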